10.5 Data and Safety Monitoring

A DSMC will not be established for the pilot study. The data and safety monitoring will be the responsibility of the investigators and medical monitor, reviewing the data contemporaneously.

10.6 Analyses

All descriptive statistics will be documented in total and stratified by age, race/ethnicity, gender, risk group and assigned treatment, when applicable. This pilot study is not powered to find statistically significant differences by treatment group.

All analyses involving randomized comparisons will include all randomized participants who received the first (**confirmed**) dose of study treatment, according to a modified intention-to-treat approach. However, as the study is blinded, the use of a modified intention-to-treat approach should not introduce bias into the comparison of randomized arms in this pilot study or in future larger-scale studies.

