6.2.4 Documentation from a health care/provider encounter - Remote

If the screening evaluation indicates either an encounter with a health care provider or symptoms greater than mild COVID-19 with shortness of breath (see table 3 above), documentation from the health care provider encounter will be obtained. This must include vital signs, SpO2 to permit classification of COVID-19 as mild or moderate which are eligible or greater than moderate which are not eligible for participation. The participants consent and HIPAA authorization will be required to obtain this health information from the provider.

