6.2.7 Study Entry Visit (Day 0) - Remote

Upon receipt of the signed eIC, HIPAA authorization, and health information if required for greater than mild COVID-19, and completion of the screening and eligibility assessment for those eligible the study entry remote visit will be conducted.

Screening and entry remote visits may be combined for mild COVID-19, but moderate COVID-19 will require separate visits so the medical information from the health provider can be reviewed to ensure they qualify as moderate COVID-19. The study entry visit is a remote contact telephone contact or video conference encounter. Participants must begin study treatment within 96 hours of the onset of symptoms.

Participants will be informed that they are eligible.

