6.2.18 COVID-19 Symptom Screen

Participants will be asked about their first symptoms related to COVID-19 and their current symptoms, to document eligibility. This will include when and what symptoms the participant noticed having. This data will be collected via the Study App.

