10 STATISTICAL CONSIDERATIONS

10.1 *General Design Issues*

This is a double-blind placebo-controlled pilot trial to document safety and efficacy endpoint assessments and to determine the feasibility of community recruitment and enrollment of symptomatic adult outpatients with COVID-19.

The observational data from Wuhan comparing hospitals with and without the use of this TCM demonstrated a reduction of 10% progression without this TCM to 2-5% with this TCM. A key difference in patient care in the US is that patients with mild and moderate symptoms are staying home having been asked to self-quarantine. Initial data on hospitalization rates in the US in early 2020 points to rates of above 20%.

A reasonable target of reduction through the use of the Xuanfei Baidu Granules would likely reduce the progression rate among those with mild/moderate symptoms, from 20% to 10%, which has the potential of an almost 30% reduction of fatalities, depending on the distribution of severity of disease at diagnosis in the population.

10.2 *Outcome Measures*

Primary and secondary outcome measures listed below will be utilized in the future studies' primary Statistical Analysis Plan, which will define the content of the Primary Analysis Report.

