10.6.2 Secondary Outcomes

Symptom severity scores will be determined from the COVID-19 symptom PROs reported daily by participants. Each symptom is rated by the participant on a scale from 0-4. Although the seriousness of the symptoms are not equal, summing the individual symptom ratings will give a rough measure of the participant's disease severity. These daily symptom severity scores will be summed over the 28-day period using area under the curve (AUC). Comparisons of this AUC, as well as weekly symptom severity scores, by age, race/ethnicity, gender, risk group and assigned treatment will be performed using Wilcoxon rank sum tests. For this, and all comparisons by demographic or treatment variables, the results will be considered for planning purposes only. Secondary outcomes 2, 3, and 4 involve compliance proportions and will be documented in total and compared by demographic and treatment variables using Fisher exact tests. Secondary outcomes 5, 6, and 7 involve event rates which will be calculated in total and compared by demographic and treatment variables using negative binomial regression. Detectable versus not detectable SARS-CoV-2 RNA from nasal swabs at days 7 and 14 will be compared by demographic and treatment variables using Fisher exact tests, and continuous measures of SARS-CoV-2 RNA (on log10 scale) will be assessed for normality and tested using t-tests or Wilcoxon rank sum tests, as appropriate.

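### Baseline severity and time since symptom onset are known by the time treatment starts, but no breakdown or comparison in 10.6 or 10.6.2 names them, and the symptom AUC is compared without adjustment

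*Combined protocol and SAP*

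**What the plan says.** **Factors named for analysis.** Section 10.6 states: "All descriptive statistics will be documented in total and stratified by age, race/ethnicity, gender, risk group and assigned treatment, when applicable". Section 10.6.2 repeats the five factors for the symptom AUC and the weekly scores: comparisons "by age, race/ethnicity, gender, risk group and assigned treatment will be performed using Wilcoxon rank sum tests". The compliance proportions are "compared by demographic and treatment variables using Fisher exact tests", and the adverse event rates are "compared by demographic and treatment variables using negative binomial regression". Section 10.6.1 allows the health-event models to be stratified or adjusted, but names no covariate.

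**What is known before treatment.** Table 3 (section 2.2) defines mild and moderate disease, and section 4.2.4 makes one or the other an entry requirement. After a provider encounter or shortness of breath, section 6.2.4 requires vital signs and SpO2 "to permit classification of COVID-19 as mild or moderate which are eligible". Section 6.2.7 adds that "moderate COVID-19 will require separate visits so the medical information from the health provider can be reviewed". The symptom screen in 6.2.18 covers first and current symptoms: "This will include when and what symptoms the participant noticed having". Treatment must start within 96 hours of onset (6.2.7).

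**What risk group means.** Sections 3.3 and 10.3 define it, the only stratification factor, by age 60 or over or a listed comorbidity.

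**The concern.** The pilot's main statistical output is planning information. Section 10.4 says that the control event rate will help to size a later trial and that it is expected to vary with the population sampled. Mild/moderate mix is one clear way in which populations differ. If the rate is reported without that mix, a planner cannot judge whether it carries over to a trial with another mix.

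Severity is not a stratification factor, so two arms of 30 can differ on it by chance, and none of the tables named in 10.6 or 10.6.2 would show it. The symptom AUC sums daily burden over 28 days, so it plausibly depends on how ill a participant is at entry and on the day of illness. An unadjusted rank test leaves that variation in the noise.

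**Working it through.** The plan gives no figure to reproduce on this point. The first check is textual and the rest is illustrative arithmetic.

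**1. Text, side by side**

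| Analysis | Factors named | Severity or onset named? |
|---|---|---|
| Descriptive breakdowns (10.6) | age, race/ethnicity, gender, risk group, treatment | No |
| Symptom AUC and weekly scores (10.6.2) | the same five | No |
| Other secondary comparisons (10.6.2) | demographic and treatment variables | No |
| Safety, hospitalization or death (10.6.1) | covariates unnamed | Open |

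**2. Inputs**
- 30 per arm (section 3); event rates 0.20 control and 0.10 XFBD (10.4).
- Moderate share 29%: the mix at one Wuhan hospital (section 2.2), the only such figure in the documents. Using it here is an assumption.
- Risk ratio k of moderate to mild: assumed, 2 to 4.

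**3. Control rate by severity.** The mild rate x solves 0.71x + 0.29kx = 0.20.
- k = 2: mild 0.155, moderate 0.310.
- k = 2.5: mild 0.139, moderate 0.348.
- k = 3: mild 0.127, moderate 0.380.

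**4. Effect of the mix.** Take k = 2.5 and x = 0.1394. The overall rate is x(1 − q + 2.5q) for moderate share q.
- q = 0.10: 0.1394 × 1.15 = 0.160.
- q = 0.50: 0.1394 × 1.75 = 0.244.

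For a later trial seeking to halve the rate (two-sided 0.05, 80% power, two proportions with pooled variance under the null), these rates need about 258 and 157 per arm, against 199 for 20% v 10%.

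**5. Chance imbalance.** Moderate counts in the two arms are independent Binomial(30, q). With q = 0.29, the probability of a difference of 5 or more is 0.20, and of 6 or more 0.12. For q from 0.15 to 0.50 the ranges are 0.10-0.25 and 0.05-0.16.

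A 5-patient difference corresponds to shares of 0.29 ± 5/60, or 0.207 and 0.373. With no drug effect, the apparent relative risk is (1 − 0.207 + 0.207k)/(1 − 0.373 + 0.373k): 0.88 for k = 2, 0.81 for k = 3 and 0.76 for k = 4.

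**6. How this sits within sampling error.** The SD of the arm difference at a 20% rate with no effect is √(2 × 0.20 × 0.80/30) = 10.3 points. The part due to severity mix is √(2 × 0.29 × 0.71/30) × (difference in rates) = 0.117 × 0.155 = 1.8 points (k = 2) up to 0.117 × 0.253 = 3.0 points (k = 3). As variance shares these are (1.8/10.3)² = 3% and (3.0/10.3)² = 8%. They lie inside the 10.3 points and are not added to it.

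**7. AUC precision.** If covariates explain a share R² of the variance, adjustment is worth a factor 1/(1 − R²) in patients: 1/0.90 = 1.11 and 1/0.75 = 1.33. The R² range of 10-25% is an assumption.

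**8. Cell sizes.** Expected moderate cases per arm: 30 × 0.29 = 8.7. Expected events: 30 × 0.20 = 6 and 30 × 0.10 = 3.

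**The case against.** The strongest reply is that little is lost. The pilot claims no power, and all comparisons are for planning only. A Wilcoxon test of randomized arms is valid without covariates. Section 10.4 already expects the control rate to vary and offers wide intervals for sensitivity analysis: 6/30 has a Wilson 80% interval of about 12-31%, which contains the whole shift from 16% to 24%. A rate in nine moderate controls would be cruder still (3/9: about 17-55%). All of this stands, and it keeps the point modest. It does not remove the need to report the mix, since a wide interval does not tell a planner which population the rate describes.

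Data quality is a fair caution. Vital signs are required only after an encounter or shortness of breath, and Table 3 lets moderate illness include any mild symptom, so severity will be unevenly documented. Patients who decline before classification may have no recorded severity, so an enrolment proportion by severity cannot be promised.

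A reader might draw three stronger conclusions that the documents do not support:
- **That the variables are excluded from every analysis.** The covariates in 10.6.1 are open.
- **That section 10.1 concedes the whole point.** It makes the projected fall in fatalities vary, "depending on the distribution of severity of disease at diagnosis in the population". It does not say that the relative effect differs between mild and moderate patients, and it is silent on time since onset.
- **That severity imbalance adds error to the binomial SD.** Step 6 shows that it is a component of that SD.

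**Conclusion.** The point holds in a limited form. Both variables are available by the first dose, neither is named in 10.6 or 10.6.2, risk group does not cover them, and the AUC comparison is unadjusted. This is a missed gain in precision and transparency. It does not invalidate any test.

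The sizes depend on assumptions. The shift in control rate from 16% to 24% needs a 2.5-fold risk in moderate disease and moderate shares of 10% and 50%. The Wuhan source of the 29% share is not shown to use Table 3's definitions, and it reports no progression, so it gives no evidence of a severity gradient. The 11-33% gain for the AUC needs an R² of 10-25%. The onset half of the point rests on the AUC argument alone and is limited by the 96-hour window. The change is still worth making, because it costs little and bears on the pilot's stated planning purpose.

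**What to change.** 1. In 10.6, add baseline severity (mild or moderate, Table 3) and days from first symptom to first dose to the breakdown factors. Tabulate the 42-day event rate and the AUC by severity and arm, so that the control rate is reported with its case mix.
2. In 10.6.2, compare the AUC between arms with a rank-based ANCOVA (or a proportional odds model) containing arm, baseline severity and days since onset. Keep the Wilcoxon test as a sensitivity analysis.
3. In 10.6.1, state that the 42-day event is tabulated by severity without multi-covariate adjustment, since about 6 and 3 events cannot support it. Name in advance any covariates for the safety models.
4. Report severity among screen failures (6.2.5) only where it was captured.

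The cost is plan wording and a few tables before unblinding. For enrolled participants the inputs are already collected, and the sample size stays at 60. The drawbacks are moderate cells of about 9 per arm if 29% are moderate, and less certain severity in participants without a provider encounter. The tables should show how many classifications rest on provider records.

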10.6.1 Primary Outcome Measure

The first two primary outcomes involve participant enrollment, and these results will help us to plan recruitment for a subsequent larger clinical trial. For example, these results may indicate that special efforts may be needed in the future to recruit certain underrepresented populations. The second two primary outcomes involve health events that will be analyzed with logistic or negative binomial regression models stratified and/or adjusted for covariates, for future planning purposes only.

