Wuhan Experience: Wuhan Jiangxia *Fangcang* Hospital used TCM prescriptions and other traditional methods (such as acupuncture, guasha, medicinal patches, etc.) in the treatment of COVID-19 while continuing the patient's previous conventional medicines for underlying health conditions. From February 14th to March 10th, the hospital treated a total of 564 patients with mild (71%) and moderate (29%) COVID-19. Upon hospitalization, approximately 30% of the patients had symptoms of fatigue and shortness of breath, while another approximately 40% had cough. Within the 14-day treatment and subsequent observation period, 482 patients recovered and were discharged. Among the patients admitted, none of their conditions progressed to severe or critical. It is of note that at Wuhan Jiangxia *Fangcang* Hospital, two main prescriptions with the addition of other TCM treatment modalities were used. The medical staff was also free of infection [personal correspondence with [name] [name] dated March 31, 2020]

For the *Xuanfei Baidu* prescription, which was given to 273 patients, none of them progressed to severe or critical condition. 250 patients achieved two consecutive negative viral RNA tests in which the average time frame was about 11.02 ± 3.59 days, with a 95% confidence interval (CI). 230 patients saw a significant improvement in their CT scans in about 13.13 ± 4.20 days with a CI 95%. [personal correspondence with [name], dated April 28, 2020]

At another *fangcang* hospital which had 330 patients, TCM was not used or if used, in an unstandardized manner, and 32 patients (9.7%) of those patients progressed to severe or critical condition. Other *fangcang* hospitals that utilized TCM prescriptions also saw a decrease in patients' progression of disease to approximately 2-5%. [personal correspondence with [name] [name] dated March 31, 2020]

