4.3.7 Known allergy/sensitivity or any hypersensitivity to components of XFBD

4.3.8 Active drug or alcohol use or dependence that, in the opinion of the site investigator, would interfere with adherence to study requirements.

4.3.9 Has known prior kidney disease.

4.3.10 Has known cirrhosis, acute liver disease or uncontrolled chronic liver disease.

4.3.11 Has known severe coronary artery disease.

4.3.12 Has known narrow angle glaucoma.

4.3.13 Has greater than two or a single uncontrolled underlying comorbid condition including cardiovascular disease (coronary artery disease, heart failure, valvular heart disease), hypertension, diabetes, chronic lung disease, chronic kidney disease, chronic liver disease, immunocompromised (HIV or daily users of more than 5 mg/day of prednisone), prior organ transplant.

4.3.14 Fulfils the FDA EUA criteria of at high risk for progressing to severe COVID-19. This includes high-risk individuals specified in the EUA who meet at least one of the following criteria: Body mass index (BMI) \geq 35; Chronic kidney disease; Diabetes mellitus; Immunocompromising condition/immunosuppressive disease; Currently receiving immunosuppressive treatment; Aged \geq 65 years; or Aged \geq 55 years and have: Cardiovascular disease, or Hypertension, or Chronic obstructive pulmonary disease/other chronic respiratory disease. If the patient is not able to receive the EUA agent because of unavailability this exclusion may be waived.

4.3.15 Women who are currently pregnant or breastfeeding.

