10.4 Sample Size and Accrual

Pilot studies have many important purposes, as described in the objectives for this study (sections 1.1, 1.2, and 1.3). However, the use of pilot studies to determine effect sizes for future larger studies is not recommended since such estimates tend to be both biased and very unstable due to the small pilot study size.(75) We illustrate this graphically for this study in Figure 1. Our current estimate is that the event rates in the control and XFBD groups will be 0.20 and 0.10, respectively. Thus, the relative risk estimate is 0.50. If these estimates are in fact attained in the pilot study, it will support our assumption, yet only mildly, since the 80% confidence interval for that relative risk (given the 20% event rate in the control group) will be 0.26-0.97. Furthermore, the environment in which COVID-19 statistics are emerging is rapidly evolving due to changes in such factors as testing rates and exposure rates within subpopulations. At the time when we are putting forward a new trial proposal, we will look at the most recent data in order to make the best possible estimate for the treatment effect.

[figure not shown]
Figure 1

In addition to the relative risk, the event rate in the control group will be estimated in order to establish an appropriate sample size for a future study. Again, we will look at the most recent data available at the time of the study proposal to inform our hypothesis. The control group event rate, however, is expected to vary by the type of population sampled, so data specific to our sampling methods will be useful. As shown in Figure 2, the confidence intervals aren't narrow, yet they provide guidelines for sensitivity analyses in estimating future necessary sample sizes.

Figure 2

80% Confidence Interval by Event Rates for Control Group (N=30)

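### The 80% confidence interval of 0.26-0.97 for RR 0.50 in 10.4 is too narrow for 30 per arm: the two-sided 80% interval is 0.22-1.16 and includes 1

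*Combined protocol and SAP*

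**What the plan says.** The planning assumption is in 10.4: "Our current estimate is that the event rates in the control and XFBD groups will be 0.20 and 0.10, respectively", which the section turns into a relative risk of 0.50. Section 3 sets 30 participants per arm and replaces those who never start treatment, so 30 per arm is also the analysed number. Section 10.4 does not name the event. I take it to be hospitalization or death within 42 days, the fourth primary outcome in 10.2.1; the arithmetic does not depend on this.

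On what the pilot could show, 10.4 says: "If these estimates are in fact attained in the pilot study, it will support our assumption, yet only mildly", and continues "since the 80% confidence interval for that relative risk (given the 20% event rate in the control group) will be 0.26-0.97". No formula or interval method is stated. Figure 1 is said to illustrate the point, and Figure 2 is captioned as giving 80% intervals for the control-group rate with N=30.

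The next paragraph adds: "In addition to the relative risk, the event rate in the control group will be estimated in order to establish an appropriate sample size". The analysis section, 10.6.1, covers this outcome as one of the "health events that will be analyzed with logistic or negative binomial regression models stratified and/or adjusted for covariates, for future planning purposes only".

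**The concern.** The interval is the one numerical statement in 10.4 of how precisely the pilot would estimate the treatment contrast. With three events against six, an upper limit below 1 at the 80% level looks too tight. If the label is wrong, a reader planning the next trial would think that observing the assumed rates would separate RR 0.50 from no effect at that level, when it would not. The pilot's stated purpose is planning, so a precision figure that errs on the favourable side should be put right even though no test or decision rule depends on it.

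**Working it through.** **Inputs.** Rates 0.20 and 0.10 (10.4); 30 per arm (section 3); so 6/30 control events and 3/30 XFBD events, RR = 0.50. Printed interval: 0.26-0.97, labelled 80% (10.4).

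**Standard error.** On the log scale,

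SE(log RR) = √(1/3 − 1/30 + 1/6 − 1/30) = √0.4333 = 0.6583.

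**Reproducing the printed figure.** Solving for the multiplier from each printed limit:

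- lower: ln(0.50/0.26)/0.6583 = 0.993
- upper: ln(0.97/0.50)/0.6583 = 1.007

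Both are 1 within rounding. Setting the multiplier to exactly 1 gives 0.50 × exp(±0.6583) = 0.259 to 0.966, which rounds to 0.26-0.97. Two-sided normal coverage of ±1 SE is 68.3%.

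**The 80% interval.** The two-sided 80% multiplier is 1.2816:

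0.50 × exp(±1.2816 × 0.6583) = 0.50 × exp(±0.8436) = 0.215 to 1.162.

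**Does another 80% method give the printed pair?** None of those tried does.

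| Method, 80% | Limits |
|---|---|
| Log-Wald | 0.215-1.162 |
| Score | 0.217-1.133 |
| Log with 0.5 added | 0.246-1.179 |
| Log, t multiplier (58 df) | 0.213-1.174 |
| Log, Poisson variance | 0.202-1.237 |
| Delta method on the RR scale | 0.078-0.922 |
| Odds ratio instead of RR | 0.168-1.178 |
| One-sided multiplier (0.8416) | 0.287-0.870 |
| Control rate fixed at 0.20: log | 0.248-1.009 |
| Fixed control: Wilson | 0.247-0.961 |
| Fixed control: Agresti-Coull | 0.233-0.975 |
| Fixed control: logit | 0.242-0.975 |
| Fixed control: Jeffreys | 0.241-0.944 |
| Fixed control: normal approximation | 0.149-0.851 |
| Fixed control: Clopper-Pearson | 0.187-1.047 |
| Fixed control: exact test inversion | 0.258-1.020 |

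**Sample size that the printed width implies.** At these rates SE² = (1/0.10 − 1 + 1/0.20 − 1)/n = 13/n per arm.

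- For an 80% interval as narrow as the printed one: n = 13 × (1.2816/0.6583)² = 49.3, or 48.6 to 49.9 if solved from the rounded limits. About 49 per arm.
- For the 80% upper limit to fall below 1: n = 13 × (1.2816/ln 2)² = 44.4, so 45 per arm.

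The plan has 30.

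**The case against.** **Fixed control rate.** The printed sentence conditions on a 20% control rate, which could mean that the rate is treated as known. Several 80% intervals then fall just below 1 (Wilson 0.247-0.961, for instance). But none reproduces 0.26-0.97, and the next paragraph of 10.4 says that the control rate is itself to be estimated. Treating it as known understates the uncertainty of a 30 v 30 comparison. The delta-method interval also lies below 1, but it is symmetric about a ratio based on three and six events and is far from the printed lower limit. What stands is that the ±1 SE origin is an inference, though a close one.

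**Does a conclusion collapse?** A reader might infer that 10.4 rests a claim of benefit on the interval excluding 1, so that its reasoning fails. The text does not support that. The clause giving the interval most naturally explains why support would be only mild, in a paragraph warning that pilot estimates are unstable. The assumption in question is RR 0.50, and 10.4 nowhere claims to exclude RR = 1. A wider interval strengthens the paragraph's caution.

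**Does anything depend on it?** Little. Section 10.6 says that the pilot is not powered for treatment differences, 10.4 advises against taking effect sizes from pilots, and the 60 participants are not derived from the interval. This limits the consequence; it does not make the number right.

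**Empty arms.** A reader might also infer that the regression in 10.6.1 is likely to fail because an arm has no events. At the planned rates the chance is 1 − (1 − 0.80³⁰)(1 − 0.90³⁰) = 4.4%. It rises to 25% at 10%/5% and 56% at 10%/2%, the range in 10.1 ("demonstrated a reduction of 10% progression without this TCM to 2-5% with this TCM"), but those figures are observational and count progression, not hospitalization. Section 10.6 already calls for descriptive statistics by assigned treatment, and the contrast is for planning. This is not a defect on the same footing.

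**Conclusion.** The 80% label on 0.26-0.97 is wrong for two arms of 30. The two-sided 80% interval at the assumed rates is 0.22-1.16 by the log-Wald method and 0.22-1.13 by the score method; both include no effect. On the log scale the printed interval is 1/1.2816 = 78% as wide as it should be, and it corresponds to about 68% coverage.

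This rests on observed counts of exactly 6/30 and 3/30 and on both rates being estimated. That the authors used ±1 SE is inferred from agreement to two decimals. The figures could not be read in the text reviewed, so no error in Figure 1 or Figure 2 is alleged. The practical consequence is limited: design, sample size and analysis are unaffected, and what changes is how informative the pilot appears.

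**What to change.** In 10.4, replace 0.26-0.97 with 0.22-1.16 and name the method. Wording such as:

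> If these rates are observed (6/30 and 3/30), the two-sided 80% log-Wald interval for the relative risk would be 0.22-1.16. Such a result would be compatible with a relative risk of 0.50 and, at the 80% level, also with no effect.

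Alternatively, keep the printed limits and label them as about 68% (±1 SE).

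Check that Figures 1 and 2 were drawn at the 80% level, that is, with 1.2816 wherever a normal-approximation interval is used.

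The cost is a wording change in one section and possibly redrawn figures. The number of participants, strata and data collection stay as they are. The only downside is that the stated precision looks less favourable. As an optional extra, separate from this point, 10.6.1 could say how the contrast will be reported if an arm has no events.
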